### 3.2.3 Secondary Efficacy Analyses

Any improvement observed by the investigator during upper gastrointestinal (UGI) and lower gastrointestinal (LGI) visualization (i.e. endoscopy and colonoscopy) at the 6 and 12-month study visits will be described using the variables UGI Observed Improvement (UGIOI), and LGI Observed Improvement (LGIOI). Each patient will have one pair of UGIOI and LGIOI outcomes.

UGIOI and LGIOI are binary outcomes derived from numerical determinations (henceforth, “investigator change scores” or more briefly, “scores”) assigned by the investigator during each procedure, using a scale (-2, -1, 0, +1, +2) which corresponds, respectively, to the investigator’s overall qualitative assessment of: much worse, worse, no change, improved, much improved. At the month 6 procedures the investigator scores UGI and LGI findings as changes from baseline. At the month 12 procedures, the UGI and LGI findings are scored relative to the month 6 procedures.

The UGIOI (and respectively, the LGIOI) secondary endpoint independently summarizes the corresponding 6- and 12-month investigator change scores according to whether or not there was *any positive improvement* at either month 6 (compared to baseline) or at month 12 (compared to baseline or month 6), under the condition that there be *no worsening at either timepoint* (compared to the preceding timepoint). Here are the specific possibilities (where “Improvement” stands for either the UGIOI or LGIOI secondary endpoint):

- If the 6-month score is -2 or -1, Improvement=NO irrespective of the 12-month score.
- If the 6-month score is 0, then Improvement=YES if and only if the 12-month score is +1 or +2. Otherwise Improvement=NO.
- If the 6-month score is +1 or +2, then Improvement=YES if and only if the 12-month score is greater than or equal to 0. Otherwise Improvement=NO.

Any patient who drops out of the study before the month 12 assessment will be considered Improvement=NO.

These binary UGIOI and LGIOI secondary efficacy endpoints will be compared in a manner analogous to the primary analysis, using the same two primary treatment comparisons (1: CPP-1X placebo + sulindac active vs. CPP-1X active + sulindac active; and 2: CPP-1X active + sulindac placebo vs. CPP-1X active + sulindac active), and conditioning on the three disease site strata (Rectum/Pouch Polyposis, Duodenal Polyposis, Pre-colectomy). The null hypothesis of no association between treatment group and Improvement endpoints will be tested using the exact Mantel-Haenszel procedure for combining the evidence contained in the fourfold tables (Treatment=Single agent vs. Combination cross-classified by Improvement=YES vs. NO) across the three strata. For each of the two treatment comparisons, exact Mantel-Haenszel p-values will be calculated for both the UGI and LGI assessments (using the point-probability method based

on the convolution of three independent central hypergeometric distributions; see [1]).

The overall type I error for the secondary efficacy analysis will be controlled using the Hochberg step-up method for multiple comparisons[2]. This analysis will be performed in the ITT population. The primary analysis will serve as a gatekeeper to control the overall type I error rate at 0.05 for both primary and secondary analyses. That is, significance for the secondary efficacy analysis will be declared only if the primary p-value is 0.05 or less, when the p-values are tested sequentially per the Hochberg method[2].

Further analyses of the secondary endpoints may be conducted to evaluate and provide additional evidence to support its validity and confirm its clinical relevance.

### 3.2.4 Other Secondary Outcomes

To explore how study treatment group relates to other efficacy outcomes, genotype, phenotype, disease locations and endoscopic findings, additional analyses are planned. These analyses will be performed in the ITT group, the Per Protocol Group, and other defined subgroups (see Section 4 Populations for Analysis) wherever possible and will all be clearly noted as such.

The UGIOI and LGIOI outcomes will be tabulated and summarized using the month 6 visit scores, alone. Similarly, the UGIOI and LGIOI outcomes will tabulated and summarized across all study visits.

As both part of the primary analysis, and further explored in these additional analyses, median time to event for each treatment group will be determined. This will be explored for each of the study populations (i.e. ITT, per protocol, and others), study disease stratum groups, and in the Disease Site subgroups (see below).

Pharmacokinetic data (plasma concentrations measured at patient visits) will be used to estimate population pharmacokinetic parameters for the CPP-1X (eflornithine), sulindac, and CPP-1X (eflornithine) + sulindac treatment groups (i.e. for each analyte for those patients on combination treatment).

The subcategories of FAP events will be explored by disease stratum groups, and by Disease Site subgroups (see below). The subcategories of FAP events include:

**Table 3.3 Disease Site Subgroups**

No	Group	Description
1	Disease Progression Indicating Need for Colectomy with IRA or Total Procto-Colectomy	Applies only to subjects with FAP surgical status of precoleectomy (field name: DIAGSXST, code 1)
2	Excisional intervention by surgical snare or trans-anal excision to remove any polyp $\geq 10$ mm in size (per pathology report) and/or pathologic evidence of high grade dysplasia	Excisional intervention does not apply to subjects with FAP surgical status of colectomy with ileostomy (field name: DIAGSXST, code 4) or subjects with FAP surgical status of precoleectomy (field name: DIAGSXST, code 1). For all remaining subjects, all $>5$ mm polyps must have been removed at baseline also

No	Group	Description
		High grade dysplasia does not apply to subjects with FAP surgical status of colectomy with ileostomy (field name: DIAGSXST, code 4)
3	Disease Progression Indicating Need for Proctectomy	Does not apply to subjects with FAP surgical status of proctocolectomy with ileal pouch anastomosis (IPAA) (field name: DIAGSXST, code 3) or FAP surgical status of colectomy with ileostomy (field name: DIAGSXST, code 4)
4	Disease Progression Indicating Need for Pouch resection	Does not apply to subjects with FAP surgical status of precolectomy (field name: DIAGSXST, code 1). or FAP surgical status of colectomy with ileostomy (field name: DIAGSXST, code 4) or FAP surgical status of colectomy with ileorectal anastomosis (IRA) (field name: DIAGSXST, code 2)
5	Development of cancer in rectum or pouch	Does not apply to subjects with FAP surgical status of colectomy with ileostomy (field name: DIAGSXST, code 4)
6	Progression in Spigelman Stage to more advanced stage (Stage 2, 3, 4)	Does not apply to subjects without duodenum (determined by abdominal surgical procedure of duodenectomy, duodenohemipancreotomy, or Whipple procedure (field name SXPROC) and screening/baseline upper GI endoscopy not done (field name UGIND, Boolean data type)
7	Disease Progression indicating need for excisional intervention (sub-mucosal resection, trans-duodenal excision, duodenectomy, ampullectomy, Whipple procedure)	Does not apply to subjects without duodenum (determined by abdominal surgical procedure of duodenectomy, duodenohemipancreotomy, or Whipple procedure (field name SXPROC) and screening/baseline upper GI endoscopy not done (field name UGIND, Boolean data type)
8	Development of cancer in duodenum	Does not apply to subjects without duodenum (determined by abdominal surgical procedure of duodenectomy, duodenohemipancreotomy, or Whipple procedure (field name SXPROC) and screening/baseline upper GI endoscopy not done (field name UGIND, Boolean data type)
9	Spigelman stage (no progression)	Does not apply to subjects without duodenum (determined by abdominal surgical procedure of duodenectomy, duodenohemipancreotomy, or Whipple procedure (field name SXPROC) and

No	Group	Description
		screening/baseline upper GI endoscopy not done (field name UGIND, Boolean data type)
10	>= 10 mm polyp in rectum pouch	Does not apply to subjects with FAP surgical status of colectomy with ileostomy (field name: DIAGSXST, code 4) or subjects with FAP surgical status of precolectomy (field name: DIAGSXST, code 1). For all remaining subjects, all >5 mm polyps must have been removed at baseline.
11	High grade dysplasia (rectum-pouch)	Does not apply to subjects with FAP surgical status of colectomy with ileostomy (field name: DIAGSXST, code 4)

These subcategories will be analyzed within the assigned disease strata (i.e. assigned at time of randomization). Separately, they will be analyzed by Disease Site, according to the concept of “the patient as a whole” meaning that *all known disease sites will be considered* because patients more often than not have more than one diseased organ system. For example, a patient randomized to treatment in the Duodenal Polyposis stratum who is also known to have colonic polyps will appear in the analyses for both Disease Site subgroups (Duodenal and Colonic). The total number of patients in the Duodenal Disease Site subgroup will include, for example, all patients randomized in the Duodenal Polyposis stratum + all other patients with known duodenal disease (irrespective of whether they have rectal/pouch disease). A similar approach will be taken for the Rectum/Pouch Polyposis group and Pre-colectomy strata.

The presence or absence of ODC polymorphisms, including the single nucleotide polymorphisms (SNPs) rs2302615 and rs2302616 and their relation to treatment group and outcome will be tested with the likelihood ratio test.

The excretion of 5 urinary polyamines (diacetylspermine, n1-acetylspermidine, n8-acetylspermidine, decarboxylated SAM, and putrescine) will be assessed in relation to treatment group and outcome, using the single point concentration data gathered from the urine samples harvested at each study visit.

Patient reported health related quality of life measures will be evaluated using HRQoL (see Section 5.6 Health Related Quality of Life (HRQoL) Statistical Methods for more details).

Tissue and dietary polyamine levels, as collected at patient study visits will be analyzed together with the results of the dietary questionnaires (see Section 5.7 Dietary Assessment) and related to treatment group and study outcomes.

Safety outcome data and analyses are described in Section 5.5.5 Assessment of Toxicities.

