### **6.1. Patient Characteristics for Eligibility, Inclusion Criteria**

1. Diagnosis of phenotypic classical FAP with disease involvement of the duodenum and/or colon/rectum/pouch.
  - a) Genotype: APC mutation (with or without family history) required
  - b) Classical FAP Phenotype: 100's to 1,000's of colorectal adenomatous polyps, usually appearing in teenage years
2. UGI endoscopy/LGI endoscopy (proctoscopy/colonoscopy) performed within 30 days of randomization.
3. Patients with an intact colon/rectum and prophylactic surgery is being considered as a stratification site.
4. Rectal/pouch polyposis as a stratification site as follows:
  - 4.a At least three years since colectomy with IRA/proctocolectomy with pouch, and demonstrating polyposis as defined by Stage 1, 2, 3, of the proposed InSiGHT 2011 Staging System (Appendix B) and summarized as follows:

Stage 1: 10-25 polyps, all  $< 5$  mm

Stage 2: 10-25 polyps, at least one  $> 1$  cm

Stage 3:  $>25$  polyps amenable to complete removal, or any incompletely removed sessile polyp, or any prior evidence of high grade dysplasia, even if completely removed. [Note: For staging purposes only.]
  - 4.b **For all subjects, any rectal/pouch polyps  $> 5$  mm must be excised at "baseline".**
5. Duodenal polyposis as a stratification site; one or more of the following:
  - 5.a Current Spigelman Stage 3 or 4. (Refer to Appendix A for Modified Spigelman Score and Classification table).
  - 5.b Prior surgical endoscopic intervention within the past six months for Spigelman Stage 3 or 4 that may have been down staged to Spigelman 1 or 2.
6. Hematopoietic Status (within 30 days prior to randomization):
  - a) No significant hematologic abnormalities
  - b) WBC at least  $3,000/\text{mm}^3$
  - c) Platelet count at least  $100,000/\text{mm}^3$
  - d) Hemoglobin at least  $10.0 \text{ g/dL}$
  - e) No history of clinical coagulopathy

7. Hepatic Status (within 30 days prior to randomization):
  - a) Bilirubin no greater than 1.5 times ULN
  - b) AST and ALT no greater than 1.5 times ULN
  - c) Alkaline phosphatase no greater than 1.5 times ULN
8. Renal Status (within 30 days prior to randomization):
  - a) Creatinine no greater than 1.5 times ULN
9. Hearing:
  - a) No clinically significant hearing loss, defined in Section 6.2, number 9.
10. If female, neither pregnant nor lactating.

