## 6.2. Exclusion Criteria

1. Prior pelvic irradiation.
2. Patients receiving oral corticosteroids within 30 days of enrollment.
3. Treatment with other investigational agents in the prior 4 weeks.
4. Use of other non-steroidal anti-inflammatory drugs (such as ibuprofen) exceeding 4 days per month, in the prior 6 weeks.
5. Regular use of aspirin in excess of 700 mg per week.
6. Treatment with other FAP directed drug therapy (including sulindac or celecoxib, fish oil) within 12 weeks of study enrollment.
7. Hypersensitivity to cyclooxygenase-2 inhibitors, sulfonamides, NSAIDs, or salicylates; NSAID associated symptoms of gastritis.
8. Patients must not have cardiovascular disease risk factors as defined below.
  - Uncontrolled high blood pressure (systolic blood pressure  $> 150$  mm Hg);
  - Unstable angina;
  - History of documented myocardial infarction or cerebrovascular accident;
  - New York Heart Association Class III or IV heart failure (Refer to Appendix C);
  - Known uncontrolled hyperlipidemia defined as LDL-C  $\geq 190$  mg/dL or triglycerides  $\geq 500$  mg/dL.
9. Patients with significant hearing loss are not eligible for study participation as defined below.
  - Hearing loss that affects everyday life and/or for which a hearing aid is required.
10. Intact colon/rectum or retained rectum or ileal pouch:
  - a) cancer on biopsy
  - b) high grade dysplasia found on polyp biopsy where the polyp is not completely removed
  - c) a large polyp ( $> 1$  cm) not completely removed.
11. Duodenal cancer on biopsy.
12. Intra-abdominal desmoid disease, stage III or IV (staging criteria in Appendix D).
13. Inability to provide informed consent.

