### **8.2.14. Definition of FAP-Related Events or Serious and Unexpected Toxicity**

The time from the date of randomization to the date of the first occurrence of any FAP-related event at any disease site (colon/rectum/pouch, duodenum) will lead to discontinuation of the study treatment. Follow-up of the subject for FAP-related events will continue, per protocol, until the end of the 30 day post-treatment.

FAP-related primary events by disease site are as follows:

1. Pre-operative, intact colon:
  - a) Disease progression^ indicating need for colectomy with IRA or total proctocolectomy
2. Rectum or pouch events include one or more of the following:
  - a) Excisional intervention by surgical snare or trans-anal excision to remove any polyp  $\geq 10$  mm in size (per pathology report) and/or pathologic evidence of high grade dysplasia.\*
  - b) Disease progression^ indicating need for proctectomy
  - c) Disease progression^ indicating need for pouch resection
  - d) Development of cancer in rectum or pouch
  - e) Death
3. Duodenal disease includes the following:
  - a) Progression in Spigelman Stage to more advanced stage (Stage 2, 3 or 4), refer to Appendix A
  - b) Disease progression indicating need for excisional intervention (sub-mucosal resection, trans-duodenal excision, ampullectomy, duodenectomy, Whipple procedure)
  - c) Development of cancer
  - d) Death

Note, excisional intervention may include open surgery, trans-anal surgery or endoscopic excisions/snare but does not include cautery ablations or hot biopsy.

\*For those subjects stratified to the duodenal group, all concurrent rectal pouch polyps  $> 5$  mm must have been removed at baseline for this event to apply.

^Disease progression is based on endoscopic evaluations compared to baseline demonstrating a clinically significant increase in number and/or size of polyps (~25% increase in disease burden), presence of a large sessile or ulcerated adenoma not amenable to removal, high grade dysplasia in any adenoma, or in-situ or invasive cancer.

Discontinuation from study treatment due to a potential treatment related serious adverse event may include the following:

- Gastrointestinal hemorrhage,  $\geq$  grade 3
- Tinnitus  $\geq$  grade 2, or clinical hearing impairment  $\geq$  grade 3

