#### **B. Duodenal Assessment**

Duodenal assessment will use a forward and/or side-viewing endoscope with video images captured for subsequent review. The Spigelman classification (Appendix A) at screening will be utilized to stage the initial extent of disease and assess subject eligibility. A side-viewing scope may be used to improve assessment of the ampulla of Vater/papilla. Ampullary biopsies (with histology) and snare excisions will be performed per the protocol, Investigator Manual, and the institution’s standard of care and the results of these procedures will be used as the subject’s baseline Spigelman classification. Further details will be provided in the Imaging Manual.

The screening stage will be the initial Spigelman Stage (extent of polyposis combined with histology) and the baseline Spigelman Stage will be the post-snare intervention.

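### SAP Table 3.3 keeps subjects with a baseline Spigelman Stage of 4 in the stage-progression and no-progression rows, although no higher stage exists for them to reach

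*SAP*

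**What the plan says.** **The event.** Protocol 8.2.14 lists, among the duodenal events, "Progression in Spigelman Stage to more advanced stage (Stage 2, 3 or 4". SAP Table 3.3 carries this over as row 6, "Progression in Spigelman Stage to more advanced stage (Stage 2, 3, 4", and adds row 9, "Spigelman stage (no progression". The description column for both rows removes only subjects who have no duodenum.

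**The scale.** Protocol Appendix A defines Stages 0 to 4. Stage 4 is 9 to 12 points, and 12 is the maximum score.

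**Entry.** Protocol 6.1 item 5.a admits "Current Spigelman Stage 3 or 4". Item 5.b admits subjects treated within the past six months for Stage 3 or 4 disease "that may have been down staged to Spigelman 1 or 2". The only exclusion criterion in Protocol 6.2 about duodenal neoplasia is "Duodenal cancer on biopsy".

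**Baseline.** Under Protocol 9.1 part B, "the baseline Spigelman Stage will be the post-snare intervention". The same section says that "snare excisions will be performed per the protocol, Investigator Manual, and the institution’s standard of care". It sets no requirement that a Stage 4 subject reach a lower stage before baseline.

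**Who is counted.** The subcategories are analysed within the randomised strata and again by disease site. The duodenal disease-site subgroup takes in everyone with known duodenal disease, with no limit on stage (SAP 3.2.4, text after Table 3.3).

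**The concern.** Elsewhere, Table 3.3 states who can have each event. Rows 1 to 5, 10 and 11 drop subjects by surgical status where the event cannot occur. Rows 2 and 10 also depend on what was done at the baseline endoscopy, namely removal of polyps above 5 mm. Restricting a row by baseline endoscopic status is thus already the SAP's practice, but rows 6 and 9 do not apply it to the top of the Spigelman scale.

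A subject whose post-snare baseline is Stage 4 adds to the row 6 denominator and can never add to its numerator. In row 9 the same subject counts as not having progressed, even if the score goes from 9 to 12. Protocol 3.1 names slower progression to Stage 3 and 4 as a hoped-for benefit of treatment, so a reader will probably take row 6 as evidence on that benefit. At stake is how this descriptive table is read, not the trial's confirmatory result.

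**Working it through.** The documents give no figure on this point, so there is none to reproduce.

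**Step 1. Can the stage rise from 4?** Appendix A scores polyp number, size and histology at 1, 2 or 3 points each and dysplasia at 1 or 3. With polyps present, the total runs from 4 (1+1+1+1) to 12 (3+3+3+3). Scores of 9, 10, 11 and 12 all map to Stage 4, so no increase in score changes the stage. The row 6 risk is exactly zero.

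**Step 2. Can such subjects be at baseline?** Item 5.a lets them in, and neither the exclusion criteria nor section 9.1 removes them. Some will be down-staged by baseline excision and can then progress again. The relevant group is therefore those at Stage 4 after any snare intervention, not those at Stage 4 on screening.

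**Step 3. Effect on the rows with an equal share in each arm.** Let s be the baseline Stage 4 share and p the progression risk among subjects below Stage 4.

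- Row 6 observed = (1 − s) × p
- Row 9 observed = 1 − (1 − s) × p
- Observed risk difference = (1 − s) × (true difference)
- Observed risk ratio = true risk ratio, because (1 − s) cancels

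Assumed true risks: 40% on a single agent and 20% on the combination. The shares are also assumptions.

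| s | Row 6, single agent | Row 6, combination | Difference | Ratio | Row 9, single agent | Row 9, combination |
|---|---|---|---|---|---|---|
| 0% | 40% | 20% | 20 points | 2.0 | 60% | 80% |
| 5% | 38% | 19% | 19 points | 2.0 | 62% | 81% |
| 10% | 36% | 18% | 18 points | 2.0 | 64% | 82% |
| 20% | 32% | 16% | 16 points | 2.0 | 68% | 84% |

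At an outer assumption of s = 40%, the difference would be 0.6 × 20 = 12 points.

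**Step 4. Unequal share.** With the same true risk p in both arms, the observed difference is p × (s in arm B − s in arm A). At p = 40%:

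- shares of 10% and 20% give 36% and 32%, a spurious gap of 4 points;
- shares of 20% and 40% give 32% and 24%, a spurious gap of 8 points.

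Here the risk ratio is distorted too. Randomisation is stratified by disease-site prognosis and not by Spigelman stage (Protocol 4.3 and 7), so only chance keeps s balanced.

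**Step 5. What is known about s.** Protocol 3.1 gives 5 to 10% at Stage 4 on screening endoscopy, and Appendix E gives 10 to 25% at Stage III/IV. Both describe FAP patients in general, before any baseline excision. Neither is the post-snare share in this trial. That share could be higher in a stratum entered through Stage 3 or 4, or lower if most subjects are down-staged.

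**Step 6. Effect on power.** This uses a two-proportion normal approximation, two-sided 5%, pooled variance under the null, assumed true risks of 50% and 25%, and s = 20%.

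- 50 per arm: 0.59 with the zero-risk subjects kept (40% vs 20%, n = 50) and 0.64 with them removed (50% vs 25%, n = 40).
- 25 per arm: 0.33 kept (n = 25) and 0.37 removed (n = 20).

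Fifty is the planned minimum for a whole trial arm, so the second line is nearer to what a stratum could supply. The gain is small in both cases.

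**The case against.** The strongest reply is that nothing confirmatory rests on these rows. Table 3.3 sits under other secondary outcomes, its subcategories are to be explored, and SAP 5.5.7 describes subgroup work as exploratory. Rows 6 and 9 have no alpha, power target, effect measure or named test. All of that stands, and it sets the priority.

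Four further objections also stand in part:

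- **Scale.** With an equal share in each arm, the risk ratio is unaffected. A general claim of bias towards no difference would be too broad; it holds for proportions and risk differences.
- **Size.** A reader might combine the background percentages and infer that a fifth or more of the duodenal stratum is at baseline Stage 4. The documents do not support this, because those figures come from separate statements about FAP in general and baseline is measured after snare excision.
- **Power.** A reader might infer a material loss of power. At a stratum-sized n, power is poor with or without these subjects.
- **Row 9.** Its label is literally true of someone who stays at Stage 4, and no passage says it will be presented as a benefit. Worsening beyond Stage 4 can still appear in row 7 (need for excisional intervention) or row 8 (cancer).

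None of this removes the structural problem. The table states who each row applies to, and for rows 6 and 9 that rule includes subjects for whom the outcome is fixed in advance. The Investigator Manual, which is not among the documents, might say more about baseline excision, but the protocol and SAP do not.

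**Conclusion.** The point holds as a low-priority correction to an exploratory table. Subjects at Stage 4 after baseline excision have zero chance of the row 6 event and fall in row 9 automatically. Row 6 proportions and risk differences are multiplied by (1 − s), and row 9 rises to match. With assumed shares of 5%, 10% and 20%, a 20-point difference reads 19, 18 and 16 points. If s differs by arm, a difference can appear where there is none.

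The conclusion rests on two things: the protocol's definition of baseline as the post-snare stage, and the absence of any stated rule that takes Stage 4 subjects below Stage 4 before baseline. The size is unknown because s is not stated.

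A reader might infer that the primary result is compromised. It is not. The stratified log-rank test uses the first FAP-related event of any kind, and a baseline Stage 4 subject can still have one through excisional intervention, cancer, death or an event at another site. The gated UGIOI and LGIOI endpoints use investigator change scores and are also untouched.

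**What to change.** In SAP Table 3.3, add to the description of rows 6 and 9 that the row does not cover subjects whose baseline (post-snare) Spigelman Stage is 4. Report the number of these subjects by arm, and show their row 7 and row 8 events separately. Tabulate change in Spigelman points for them only if the points are captured at follow-up; the documents describe staging but do not say that point totals are recorded.

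Make the change before unblinding, so that the exclusion cannot look data-driven. It needs no new visit or procedure and leaves the primary endpoint alone. The cost is one line in the table and a smaller denominator for rows 6 and 9, by an amount that cannot be judged until the baseline stage distribution is tabulated.
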